3 RESEARCH QUESTION/AIM(S)

- 1. What is the profile of children and young people referred to GID services?
- 2. What proportion of children and young people, aged 3-13 years when their referral was accepted to these services experience ongoing gender dysphoria, and go on to have physical treatment? What are the predictors of such occurrences?
- 3. What is the impact of a) physical treatment b) social transition c) co-occurring autism on, physical health, psychological wellbeing, quality of life, peer and family relationships and cost to the NHS and other public services?
- 4. What is the experience of children and young people, and their families after they are referred to GID services?

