3.2 Outcome

This research will generate important new insights about a population of children and young people who experience significant distress about their gender identity and are referred to a GID service for support and/or long-term intervention. Making as accurate an assessment as possible at a younger age has profound implications for the psychological and physical wellbeing of the individual but also for the cost to the NHS and public funds. The study will seek to identify the factors that influence this group's mental health, behavioural and emotional functioning, and quality of life. It will identify the factors that influence whether a child or young person chooses physical/endocrine treatment and compare the mental health, wellbeing and physical health outcomes for those in receipt of endocrine treatment with those of a similar age/pubertal stage not receiving such treatment. It will also explore the impact of factors such as a) co-occurring ASD, and b) a decision to socially transition, on outcomes over time.

Health economic data will be generated regarding the costs and consequences of a range of service, intervention and children and young people/family characteristics. The qualitative component of the longitudinal study will complement the quantitative elements by providing in-depth data on experience of gender diversity issues and services and how these change over time from the perspective of children and young people and their families. This will include those who do not progress through GIDs services as well as those who do.

The data generated will be used as material to develop multi-media resources to inform children and young people and their families about the differing narratives and trajectories of this group. These resources will be developed in consultation with key stakeholders and will aim to convey, in a child and family centred way, the 'human stories behind the figures'. These multi-media resources will also assist in the education of NHS commissioners and clinicians, schools and other relevant service providers, and thereby help to enhance therapies and support for children and young people and their families.

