association between the pre-specified explanatory variables and persistent or ongoing GD. Appropriate regression models will be used to investigate the explanatory variables for the secondary outcomes, physical/endocrine intervention, Mental Health (SDQ), Behavioural and Emotional Functioning (CBCL, YSR) and Quality of Life (Kidscreen 52, CHU-9D). Models will account for the repeated measures of Mental Health and Behavioural and Emotional functioning and quality of life outcomes and the relevant explanatory variables. Exploratory subgroup analyses will be carried out for the prepubertal children and children with autistic traits (as assessed using the AQ) using descriptive statistics and appropriate regression models, where possible. Physical and psychological health outcomes over time will be compared descriptively between those in receipt of hormone blockers (GnRH agonists) and those of a similar age/pubertal stage who progress through puberty without such intervention.

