- Child and Youth Resilience			
Measure (CYRM)			
- Child Health Utility 9			
Dimensions (CHU-9D)			
Dimensions (CHO-9D)			
Questionnaire assessment for	Dependent on	60 mins	Self-report
children over 12 years with capacity	age/competence		
to self-complete at T0, T1, or T2:	of child at each		
- Gender dysphoria	time point		
questionnaire (GDQ)	(between 0 and		
- Young Persons Gender	3)		
Questionnaire (DSM			
Criteria for Gender			
Dysphoria; Gender Identity;			
Background to Referral;			
Social Transition; Body			
Image & Distress;			
Relationships & Attraction)			
- Utrecht Gender Dysphoria			
Scale (UGDS; Gender			
Dysphoria Scale\)			
- Strengths and Difficulties			
Questionnaire (SDQ; brief emotional and behavioural			
screener)			
- Moods and Feelings			
Questionnaire (MFQ;			
depressive symptoms)			
- Child and Youth Resilience			
Measure (CYRM; social-			
ecological resilience)			
- Gender Identity Self			
Stigma Scale (internalised			
stigma and transphobia)			
- Kidscreen 52 items			
(KIDSCREEN-52; Child			
health and well-being)			

Identity in Children			
 Warwick-Edinburgh Mental Wellbeing Scale (WEMWBS; Mental wellbeing) Child Health Utility 9 Dimensions (CHU-9D; Quality of life) Youth Self Report (YSR; Emotional and Behavioral Functioning) 			
Physiological assessment for all participants, including those not going to a clinic: - Parents heights (at start) - Child's height - Child's weight - Child's pubertal development (RCPCH guidance on measuring puberty phase) - BMI All of the above are self-measured or measured with assistance from a parent/carer at each assessment (T0, T1, T2) using simple instructions provided by research team	3	5 – 10 mins	Self-measured
(Request for routinely collected data – not part of intervention research) Physiological assessment for participants (children and young people) receiving physical treatment with hormone blockers (GnRH agonists) and/or cross-sex hormones: - Parent's heights (Clinical measure) - CYP height, sitting height, bi-acromial width, bi-iliac width, weight (clinical measures) - BMI (value derived by calculation) - Pubertal Tanner staging (Clinical examination)	3	N/A	University College London Hospitals (UCLH) NHS Foundation Trust

- Body composition (Tanita bioelectrical impedance analyser)	
Radiological measures - Bone densitometry (Dexa Scan) - Bone age (X-ray of left hand & wrist)	

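### The protocol asks for the impact of physical treatment, but the only analysis it states for the hormone-blocker contrast is descriptive, with no baseline adjustment and no time point for judging similar pubertal stage

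*Protocol*

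**What the plan says.** Protocol section 3 puts the question causally: "What is the impact of a) physical treatment b) social transition c) co-occurring autism on, physical health, psychological wellbeing, quality of life", followed by relationships and cost. Section 3.2 promises that the study will "compare the mental health, wellbeing and physical health outcomes for those in receipt of endocrine treatment with those of a similar age/pubertal stage" who are untreated.

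Section 7, part a) states how this contrast will be analysed: "Physical and psychological health outcomes over time will be compared descriptively between those in receipt of hormone blockers (GnRH agonists"). The other side of the comparison is described as "those of a similar age/pubertal stage who progress through puberty without such intervention". It describes no procedure for choosing the comparators, no assessment at which age and stage are to be alike, and no covariates.

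The same paragraph also plans models: "Appropriate regression models will be used to investigate the explanatory variables for the secondary outcomes, physical/endocrine intervention, Mental Health (SDQ") and the behaviour and quality-of-life scales. It adds: "Models will account for the repeated measures of Mental Health and Behavioural and Emotional functioning and quality of life outcomes and the relevant explanatory variables". The explanatory variables are not listed, and physical intervention appears there as an outcome. The cost and QALY models later in section 7 name active contact with the service as the exposure. The only covariate adjustment that section 7 names is for predictors of missingness.

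Appendix 3 records height, weight, BMI and puberty by self-measurement at T0, T1 and T2 under the label "Physiological assessment for all participants, including those not going to a clinic". Bone density, bone age, blood tests and clinical Tanner staging are requested from the clinic for treated children only.

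**The concern.** A question about impact needs a comparison in which treated and untreated children would have had similar outcomes without treatment. The protocol does not expect that by default: research question 2 looks for predictors of physical treatment, and section 3.2 looks for the factors behind choosing it. Any such factor that also affects mental health or quality of life will show up in a raw contrast as if it were an effect of treatment. Similarity on age and pubertal stage deals with two such factors and leaves the rest.

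The second gap is timing. Section 1 describes the treatment as suppressing puberty, and stage is recorded at all three assessments. Stage before treatment is a legitimate basis for comparison; stage after treatment is partly a result of it. Section 7 does not say which is meant.

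Section 3.2 and the dissemination text that follows it expect the findings to shape NHS treatment protocols and guidance, so whether the result is an effect or a description matters.

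**Working it through.** **1. The protocol's own figures (section 9.2.1).**
- Recruitment: 0.70 × 912 = 638.4, stated 638.
- Complete follow-up: 638 × 0.80 = 510.4, stated 510.
- Gender dysphoria events: 510 × 0.40 = 204, as stated.
- 95% CI for 40%: 0.40 ± 1.96 × √(0.40 × 0.60 / 510) = 35.75% to 44.25%, as stated.
- 95% CI for 21%: 17.47% to 24.53%, against the stated 17.45% to 24.55%, a rounding difference.

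The sample-size section sets no alpha, power or effect size for the treated-versus-untreated contrast.

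**2. Size of the groups.** 0.21 × 510 ≈ 107 treated, leaving 403 untreated. Across the stated interval for 21%, the treated number runs from 89 to 125. Here 403 is an upper limit, because section 7 restricts comparators to like age or stage. The 21% covers any physical intervention during follow-up, not blockers alone, and includes late starters.

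**3. Best-case precision, in SD units.**
- SE = √(1/107 + 1/403) = 0.109.
- 95% CI half-width = 1.96 × 0.109 = 0.21 (0.20 to 0.23 across 125 to 89 treated).
- Detectable difference (assumed two-sided 5%, 80% power) = 2.8 × 0.109 = 0.30.
- With baseline adjustment at an assumed correlation of 0.6: 0.30 × √(1 − 0.36) = 0.24.

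**4. Confounding with no true effect (assumed values).** Suppose treated children start 0.5 SD worse and the baseline-to-T2 correlation is 0.6.
- Raw T2 difference: 0.6 × 0.5 = 0.30 SD worse in the treated.
- Raw change from baseline: 0.30 − 0.50 = −0.20 SD, apparently better in the treated.

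Two equally descriptive displays of the same data therefore point in opposite directions.

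The range is wide. For a binary confounder, spurious difference = (prevalence in treated − prevalence in untreated) × its effect on the outcome. The last column is how often a two-sided 5% test would reject with 107 v 403.

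| Prevalence, treated v untreated | Effect on outcome (SD) | Spurious difference (SD) | Rejection rate |
|---|---|---|---|
| 50% v 40% | 0.3 to 0.8 | 0.03 to 0.08 | 6% to 11% |
| 60% v 40% | 0.3 to 0.8 | 0.06 to 0.16 | 9% to 31% |
| 70% v 30% | 0.3 to 0.8 | 0.12 to 0.32 | 20% to 84% |

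**5. Timing of pubertal stage (simulation, assumed values, no true effect).** Stage is held in the treated and advances in the untreated; the outcome rises 0.15 SD per year of age.
- Compared within stage at treatment start: bias about 0.00 SD.
- Compared within stage at two years: bias about 0.17 SD.

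This shows only that the time point matters. The outcome in the simulation depends on age alone, so holding age as well removes the bias there. In practice, children of the same age who share a stage at follow-up would be treated children and slower-maturing untreated ones. The resulting bias depends on how maturation relates to the outcome, which the protocol does not tell us.

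**The case against.** **The regressions might already cover it.** The repeated-measures models have unlisted explanatory variables, physical treatment could be one of them, and the statistical analysis plan is not shown. So a reader might infer that impact will be studied only descriptively, and that goes further than the text. What stands is narrower: the one sentence that names this contrast fixes it as descriptive, and nowhere is treatment named as an exposure in a model of health outcomes. That is a stated method, not a detail left open.

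**Descriptive reporting can be prudent.** For a non-randomised contrast this is a fair view, but it does not fit a question worded as impact. Outcomes shown over time would also make a baseline gap visible, though visible is not the same as allowed for.

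**Matching on an altered pubertal stage.** A reader might infer that controls are matched on a stage that blockers change. The protocol describes likeness, not matching. Its description of comparators as going on through puberty untreated fits likeness at the start at least as well, because stages would diverge afterwards. The bias exists only if stage is taken after treatment starts.

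**Unequal measurement.** A reader might infer that clinic values in the treated will be set against self-measurements in the untreated. Appendix 3 collects the self-measured items in everyone and nothing says the two sources will be mixed. Section 7 simply does not limit the between-group comparison to the shared items.

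**Conclusion.** The concern holds in a limited form. The protocol asks for the impact of physical treatment, and the analysis it states for the blocker contrast cannot deliver that. It names no control beyond like age or pubertal stage and fixes no time at which that likeness is judged. Confounding by the reasons for treatment is a serious and uncontrolled risk. Conditioning on post-treatment stage is a separate and conditional one, and the two should not be merged.

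It would be too strong to say that the comparison will be biased by a known amount or in a known direction. The 0.30 and −0.20 SD figures rest on the assumed 0.5 SD gap and 0.6 correlation, and the 0.17 SD figure on an artificial model. The detectable differences of 0.30 and 0.24 SD follow from the protocol's 21% and 510, with assumed error rates and, for the second, the assumed correlation; they are best cases. No sample-size figure in the protocol is affected. The change should be made, but it is one of analysis and wording.

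**What to change.** In section 7, part a):

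- Keep the descriptive display. Add a repeated-measures regression, or a propensity-weighted analysis, of SDQ, CBCL/YSR and quality of life with physical treatment as a time-varying exposure.
- Adjust for the outcome's baseline value, age, pubertal stage, birth-assigned sex, gender dysphoria severity and AQ. Take all of them from the last assessment before treatment start, or from a matched index assessment in the untreated. Using T0 values alone would leave confounding by changes between T0 and treatment start.
- Define likeness of age and pubertal stage at that same assessment.
- Compare physical outcomes between groups only on the self-measured items collected in everyone, and describe clinic-only measures within the treated group.
- Report adjusted associations, state the residual confounding, and do not call the result impact.

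If no adjusted analysis is wanted, the minimum is to say that this contrast is descriptive and does not answer research question 3a.

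The cost is modest extra analysis and programming. No new data are needed: children enter while awaiting their first appointment (section 9.1.1), so T0 should precede any treatment the service starts, and Appendix 3 already collects the covariates. The price in precision is a comparator group smaller than 403, so detectable differences will be larger than 0.30 and 0.24 SD.

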8 STUDY SETTING

The study will take place at the UK Gender Identity Development Service for children and young people and their families. This is the largest such service in the world and, combined with the increase in referrals in recent years, means that it is uniquely positioned to undertake research of this kind.

9 SAMPLE AND RECRUITMENT

9.1 Eligibility Criteria

Eligibility for participation will be determined by 1) referral status; and 2) age.

9.1.1 Inclusion criteria

In order for children and young people to take part in the study, they must:

- Be aged 3-13 years at the time referral was accepted;
- Have been referred to the GIDS and awaiting their initial appointment prior to first contact;
- Have parental consent;
- Speak English;
- Live in the UK.

9.1.2 Exclusion criteria

Children and young people will not be allowed to participate in the study, should they:

- Be aged 13 years or older at the time of referral;
- Refuse to assent to take part, or not have parental consent;
- Not meet the above inclusion criteria

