2 RATIONALE

Very little is known overall about the profile of children and younger adolescents referred to Gender Identity Development (GID) services. At present, we are unaware, both in the UK and internationally, of the outcomes and likely trajectories of children and young people presenting to these services.

A key question for the NHS pertains to the proportion of gender diverse children and young people presenting to services who later go on to receive treatment with hormone blockers, and which factors predict this. Additionally, major knowledge gaps currently exist in relation to the immediate and long-term impact of a) physical treatment commencing in early puberty b) early social transition c) and co-occurring Autistic Spectrum Disorder (ASD).

This study will characterise the entire cohort of children and younger adolescents aged between 3 and 13 years at the time of referral to a GID service. It will help us develop a greater understanding of the individual differences in those referred to the service. The findings generated from this research will enable services to provide better, more individualised care, which will provide immediate benefits to patients and their families.

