9.2 Sampling

9.2.1 Size of sample

a) Quantitative study

A total of 638 children and young people will be recruited to the study. This target is based on recruiting 70% of anticipated referrals to the GID service of children and young people age 13 years or under over an 18 month period. Of an estimated total of 3,298 referrals to the service in 18 months, 912 referrals pertained to children and young people aged 13 years or younger in 2016-2017. Allowing for 20% attrition and assuming 40% prevalence of GD (29) a total of 204 GD events are expected to be observed in the 510 children with complete follow-up in the cohort study. This will allow us to fit a logistic regression model with the 14 explanatory variables and estimate the resulting 19 regression coefficients with adequate precision (30). The sample size of 510 will also allow us to estimate the proportion of children with GD, expected to be 40% with reasonable precision 95% CI (35.75% to 44.25%). The proportion receiving physical intervention is anticipated to be around 21% during the follow up time and this proportion can be estimated with a 95% CI (17.45% to 24.55%) (31).

b) Qualitative study

We will purposively sample a sub-set of up to 40 families (children and young people and parents) from the quantitative study for the qualitative baseline interviews. We anticipate that a sample of this size will be necessary to achieve data saturation within sub-samples of interest, particularly to include children and young people who continue to experience gender dysphoria and progress to physical

treatments, as well as to include those who do not progress to physical treatments. Sampling to the qualitative study baseline interviews will cease when saturation and adequate information power (32) is judged to have been reached.

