9.2.2 Sampling technique

a) Quantitative study

All children and young people aged 3-13 years when their referral was accepted by the GID service and awaiting a first appointment will be invited to participate in the study. This includes those currently sitting on the waiting list (n=585) and consecutive new referrals to the service (n~43 p/m) across the 18 month recruitment period. The waiting period will be divided into thirds and research effort equally extended on each third. In this way, we shall strive to treat each interval of waiting equally. Our revised strategy will be reviewed regularly and adapted should there be any change in policy towards, or service throughput of, this age group.

b) Qualitative study

Purposive sampling to the qualitative study will be informed by data from the quantitative study. A key aim is to interview CYP who subsequently go on to experience continuing gender dysphoria and progress to physical treatments, as well as CYP whose gender identity issues subsequently resolve and who do not progress to physical treatments. As these outcomes will not be known at baseline, sampling will take account of factors considered to be associated with these outcomes based on current research evidence and clinical knowledge. To address this we will sample equal numbers of CYP who have socially transitioned at baseline and equal numbers who have not socially transitioned at baseline, although we will review this strategy in the light of new evidence emerging over the course of baseline sampling. Across the whole sample we will aim to interview approximately 12 CYP with co-occurring ASD reflecting the large numbers of such CYP referred to GIDS, and approximately 6-8 black and ethnic minority CYP reflecting the UK general population. Sampling will also aim for balance in family socioeconomic status, location of GIDS and assigned gender at birth. Sampling will also be informed by the ongoing analysis of both the quantitative study data and qualitative data on an iterative basis.

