9.3 Recruitment

9.3.1 Sample identification

a) Quantitative study

Potential participants will be identified from a list of referrals received at the service. Following a request for specific information, a member of the Trust's informatics team will go through a referral list received at the service to source those aged 13 and under at the time their referral was accepted by GIDS and who are currently awaiting their first appointment. They will not need special permissions as they would routinely access this data.

b) Qualitative study

The quantitative assessments will commence prior to the qualitative study. All families will be asked to consent to be approached for participation in the qualitative study at the point of consent for the quantitative assessments. Consent to being contacted for the qualitative study, at the time of consenting for participation in the quantitative study, will be optional. The research assistants working on the quantitative study will share the details of all participants who consented to be contacted for the qualitative study with the qualitative research associate. A sub-set of families (children and young people and their parents) will be identified and recruited to participate from the consents received, as per the above sampling technique. As capacity to take part in an interview is not necessarily dependent upon age, we will explore whether children and young people display Gillick competence at the time of interview. Those who display such capacity will be asked to provide informed consent.

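### Section 9.1.2 excludes children aged 13 at referral, whom the rest of the protocol includes, so a child aged 13 at both referral and acceptance is eligible and ineligible at once

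*Protocol*

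**What the plan says.** Section 9.1 makes eligibility depend on referral status and age.

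- **Inclusion (9.1.1):** "Be aged 3-13 years at the time referral was accepted".
- **Exclusion (9.1.2):** "Be aged 13 years or older at the time of referral". A further bullet in the same list, "Not meet the above inclusion criteria", ties the two lists together, so a child has to satisfy both.
- **Invitation (9.2.2):** "All children and young people aged 3-13 years when their referral was accepted by the GID service and awaiting a first appointment will be invited".
- **Search of the referral list (9.3.1):** the informatics team is to "source those aged 13 and under at the time their referral was accepted by GIDS".
- **Rationale (section 2):** the cohort is "aged between 3 and 13 years at the time of referral to a GID service".
- **Sample size (9.2.1):** the target of 638 is 70% of a referral count described as "912 referrals pertained to children and young people aged 13 years or younger in 2016-2017".

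The study summary and sections 3, 3.1 and 5 also give the range as 3 to 13 years.

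**The concern.** Of all the places that state the age range, only the 9.1.2 bullet puts age 13 outside it. It also dates age at referral, whereas 9.1.1, 9.2.2 and 9.3.1 date it at acceptance of the referral.

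The bullet is an operative rule. Under 9.2.2 and 9.3.1 a 13-year-old is found and invited. A researcher who follows 9.1.2 must then refuse that child, and one who follows 9.1.1 may enrol the child. Enrolment breaches a written exclusion criterion, and section 10.5 requires every breach to be recorded and reported. Refusal takes out the oldest children, which changes the population behind the two headline proportions (gender dysphoria and physical intervention) and thins the older end of the comparison by age and pubertal stage in sections 3.2 and 7. If staff differ in which bullet they apply, enrolment becomes selective by age.

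**Working it through.** **1. Who is caught by the conflict.** The two lists use different dates, so the cases need to be separated.

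| Age at referral | Age at acceptance | 9.1.1 | 9.1.2 age bullet | Result |
|---|---|---|---|---|
| 12 | 12 | included | not excluded | eligible |
| 12 | 13 | included | not excluded | eligible |
| 13 | 13 | included | excluded | contradiction |
| 13 | 14 | not included | excluded | ineligible |

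The contradiction falls on children who are 13 at both dates.

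**2. Whether a reading removes it.**
- Taking 3-13 to mean up to the 13th birthday fails, because 9.3.1 and 9.2.1 count children aged 13 and under, which puts age 13 inside the range.
- Relying on the different dates fails, because section 2 includes age 13 at the time of referral, the same date that 9.1.2 uses.

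**3. The plan's own figures (9.2.1).** These reproduce:
- recruited: 0.70 × 912 = 638.4 (stated 638)
- completers: 638 × (1 − 0.20) = 510.4 (stated 510)
- events: 510 × 0.40 = 204 (stated 204)
- events per coefficient: 204 / 19 = 10.7
- 95% CI half-width for 40%: 1.96 × √(0.40 × 0.60 / 510) = 4.25 points (stated 35.75% to 44.25%)

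The arithmetic is sound, and the population it counts includes 13-year-olds.

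**4. What enforcing 9.1.2 could do to numbers.** The children to be invited are described in 9.2.2: a waiting list of 585 plus about 43 new referrals a month for 18 months.

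Pool = 585 + 43 × 18 = 585 + 774 = 1,359

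Let s be the share of this pool removed by 9.1.2. The protocol does not give s. Assume that the 70% uptake of 9.2.1 also holds for waiting-list children, which the protocol does not say.

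- Break-even: 0.70 × 1,359 × (1 − s) = 638, so s = 1 − 638 / 951.3 = 0.33.
- s = 20%: 1,087 remain; 70% gives 761, so 638 is reached and the design figures stand.
- s = 40%: 815 remain; 70% gives 571 recruited, × 0.8 = 457 completers, × 0.4 = 183 events, / 19 = 9.6 per coefficient. The half-width for 40% is 1.96 × √(0.24 / 457) = 4.5 points. Reaching 638 would need 638 / 815 = 78% uptake.

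**The case against.** The strongest reply is that the intent is plain. Every other statement of the range includes 13, candidates are drawn centrally by a search that includes 13, and all of them are to be invited. One bullet is out of line, and nothing in the protocol shows that any child was turned away because of it. This is fair as to intent, and it makes the correction easy. It does not remove the conflict, because the exclusion list is what a researcher applies at enrolment, and as written it bars children whom the search has just produced.

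Two stronger readings are tempting and are not supported.

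- A reader might infer that every 13-year-old is both eligible and ineligible. The dates differ, so a child who turns 13 between referral and acceptance passes both lists.
- A reader might infer a large loss of precision by shrinking the 912 directly. With an assumed 20% to 40% aged 13, that route gives 409 to 306 completers, 163 to 123 events and 8.6 to 6.5 events per coefficient. But 912 is the 2016-2017 referral figure used to set the target, while the pool to be approached is the 1,359 of section 9.2.2. On that pool, at the same uptake, a 20% loss costs nothing against 638, and a 40% loss costs much less than the 912 route suggests. The 20% to 40% share is itself an assumption with no support in the protocol.

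**Conclusion.** The contradiction is real, stands in the current text, and does not depend on the amendment history. It concerns children aged 13 at both referral and acceptance, on one of the two criteria that decide eligibility. It must be corrected because both rules cannot be followed for these children, and because the literal exclusion would change the population that the study sets out to describe.

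The case does not rest on lost precision. How many children are affected cannot be known from the protocol. On the 9.2.2 pool, and assuming 70% uptake for waiting-list and new referrals alike, the target survives unless more than about 33% of the pool is removed. At an assumed 40%, events per coefficient would be 9.6 against 10.7 by design, and the half-width for the 40% proportion 4.5 points against 4.25.

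**What to change.** Reconcile 9.1.2 with the rest of the protocol:

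1. State one upper age limit. The range used everywhere else implies that the exclusion should start at age 14; if the sponsor instead means to exclude 13-year-olds, then 9.1.1, 9.2.1, 9.2.2, 9.3.1 and the other statements of the range must change.
2. Use one reference date, acceptance of the referral, in 9.1.1, 9.1.2 and section 2.
3. Check the recruitment records for any 13-year-old refused under the current wording, and report the number.

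The cost is a short wording amendment, handled under section 10.2, and a check of records. The design, target and analysis stay as they are if age 13 is confirmed as eligible.
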